8.2 SAFETY AND OTHER ASSESSMENTS

8.2.1 SAFETY

1. A suicide questionnaire previously used in IRBs #14-0600 and #14-1622 will be used at each session of this study. This questionnaire tracks suicidal ideation and behavior. Participants will be asked to answer whether they have had any thoughts of hurting themselves within the past 24 hours (suicidal ideation, SI) and whether they have hurt themselves within the past 24 hours (suicidal behavior, SB). If a participant admits to experiencing either SI or SB their participation will be stopped immediately and their primary mental health care provider or family physician will be contacted. In the case that they do not see anyone for their depressive symptoms, [name] will assist the participant in seeking medical care
2. The structural MRI to be used for source localization during EEG analysis will be conducted prior to randomization. The results of the T1 weighted sMRI will be reviewed by [name] for incidental findings of malignancy. If any are found, the study team will disqualify patient from study participation and will facilitate contact with providers for medical care per [name] recommendations. Patients will complete the provided MRI screening form provided by the Biological Research Imaging Center (BRIC) prior to the sMRI screening visit.
3. A stimulation adverse effects questionnaire will be administered at the end of each stimulation session. This questionnaire will be used as a safety measure and to collect data on participant experience. This questionnaire has been used in all our previous tACS studies.
4. The Young Mania Rating Scale (YMRS) (Young, Biggs, Ziegler, & Meyer, 1978) was designed to assess the severity of manic symptoms at baseline, with the ability to reassess the individual's symptoms over time. When undergoing treatment that may affect depression symptoms, a possible effect of treatment is to alter the serotonin levels, potentially causing a manic episode. Although we do not expect such an event to occur since we are not using a medication that targets serotonin levels, we will be conducting this assessment at each evaluation as a precautionary measure. In the case a participant develops any sign of mania (YMRS > 12), [name] will conduct an acute assessment to determine if the participant is experiencing mania. In the case that a participant develops mania during the week of stimulation, their participation in the study will be stopped and their primary mental health care provider or family physician will be contacted. In the case that they do not see anyone for their depression, [name] will assist the participant in seeking medical care.

5. Urine pregnancy tests will be conducted for all female participants of reproductive age at screening and prior to stimulation on the day 1/baseline session, a negative result will be verified and documented OR a positive result will be documented and the patient will be withdrawn from the study.

To protect our participants during COVID-19, some of the assessments listed above are offered to be collected remotely over the phone or through a UNC approved video platform. These assessments include the YMRS.

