received tACS reported an increase in suicidal ideation from baseline. We will be using the Suicide Item included in the HDRS17 to assess suicide risk. Inclusion criteria states that the patient must be low suicide risk defined as a score of less than 3 on the HDRS17 suicide item, potential participants that have an above “low risk” designation will not be eligible for the study. Additionally, we will administer this as a daily questionnaire to assess suicide risk. In the case suicide risk increases after the screening visit, the participant will be asked to stop the study and will be provided with a referral to UNC Psychiatry and their mental health care or family medical doctor will be contacted. [name], Co-I, will facilitate this process.

Research within our lab has shown that alpha and theta oscillations exist in an antagonistic relationship. Therefore, an increase in alpha oscillations would result in a decrease in theta oscillations (and vice versa). In a previous tACS trial (Alexander et al., 2019), we found that alpha-tACS reduced alpha oscillations over the course of 5 days. We propose that alpha-tACS did this through synchronization of those two areas. Theta-tACS would theoretically work in an orthogonal mechanism to alpha-tACS, by suppressing alpha oscillations, rather than synchronizing it. Theoretically, theta-tACS could exacerbate underlying depression and worsen outcomes. Furthermore, traditional treatments for depression (e.g., antidepressants) run the risk of exacerbating depression symptoms as well. We will be following patients closely throughout the study as well as employ the assistance of a Data Safety and Monitoring Board, which we plan to review our blinded data every 6 months.

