5 STUDY POPULATION

5.1 INCLUSION CRITERIA

- Ages 18-65 years
- Meet the 2012 Systemic Lupus International Collaborating Clinics criteria OR the 1997 American College of Rheumatology criteria for SLE diagnosis, including testing positive ANA and/or anti-dsDNA and/or anti-ENA
- Low suicide risk (score of <3 on the Suicide Item on the HDRS17)
- Capacity to understand all relevant risks and potential benefits of the study (informed consent)
- Not experiencing manic episode; a manic episode is defined as a score > 12 on the YMRS.
- Stable on all SLE-related and psychiatric meds for 4 weeks prior to screening

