7 STUDY INTERVENTION DISCONTINUATION AND PARTICIPANT DISCONTINUATION/WITHDRAWAL

7.1 DISCONTINUATION OF STUDY INTERVENTION

Discontinuation from the week of stimulation does not mean discontinuation from the study, and remaining study procedures should be completed as indicated by the study protocol. If a clinically significant finding is identified (including, but not limited to changes from baseline) after enrollment, the investigator or qualified designee will determine if any change in participant management is needed. Any new clinically relevant finding will be reported as an adverse event (AE).

The study intervention (i.e., the 5 consecutive days of stimulation) will be discontinued for the following reasons:

- A participant develops increased suicidal risk, as determined by an acute assessment by [name].
- A participant has a YMRS score greater than to 12.
- The participant misses two consecutive days of stimulation.
- The participant misses a single day of stimulation and is unable to make it up at the end of the stimulation week.
- Any clinical adverse event (AE), laboratory abnormality, intercurrent illness or other medical condition, or situation occurs such that continued participation in the study would not be in the best interest of the participant.
- The participant meets any exclusion criteria (either newly developed or not previously recognized).
- A participant wishes to withdraw from further participation for any reason.

If the participant withdraws from the intervention, he/she will be followed through the 4 week follow-up with the designated clinical assessments to ensure participant safety:

- HDRS
- YMRS
- Suicide Questionnaire

Additional measures may be continued if deemed appropriate (e.g., EEG, cognitive tasks, Comparative Pain Scale, Pain Catastrophizing Scale).

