9.4.4 SAFETY ANALYSES

Safety will be assessed with a suicide questionnaire, the Columbia-Suicide Severity Rating Scale (C-SSRS), an adverse effects questionnaire, and the Young Mania Rating Scale (YMRS).

The suicide questionnaire is used as a screening to assess increase in suicidal ideation (SI) or suicidal behavior (SB). If a participant's responses indicate SI or SB, the participant will be contacted and an acute assessment will be completed if necessary by [name]. Any verified increases in suicidal ideation will be described in counts/percentages and compared between groups using chi-square tests.

The adverse effects questionnaire will be administered following every stimulation session, for a total of 5 administrations per participant. The adverse effects questionnaire inquires about 14 possible adverse effects associated with electrical stimulation, rated on a scale of 1 (absent) to 4 (severe). Paired t-tests

with random effect "participant" will be calculated per adverse effect to determine if there are any differences in adverse effect severity between groups (sham/placebo, alpha-tACS, theta-tACS). Severity per adverse effect will be described with mean and standard deviation.

The Young Mania Rating Scale (YMRS) will be used to assess any development of mania over the course of treatment. A YMRS score of greater than 12 indicates the possible development of a manic episode. Any participant who scores greater than 12 on the YMRS will be assessed by [name]. Any verified manic episode will be described in counts/percentages and compared between groups using a chi-square test.

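### Sections 8.2.1, 7.1 and 2.3.1 give conflicting rules for stopping a participant for suicidality, and the YMRS rule is unclear, so staff cannot tell who is stopped, who decides, and from what

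*Combined protocol and SAP*

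**What the plan says.** On suicidality, four sections of the protocol speak.

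- Section 8.2.1, item 1, gives a yes/no questionnaire at each session about thoughts of self-harm (SI) and acts of self-harm (SB) in the past 24 hours: "If a participant admits to experiencing either SI or SB their participation will be stopped immediately". The participant's own doctor is then contacted. No assessment comes first.
- Section 7.1 lists reasons for ending the intervention. One is "A participant develops increased suicidal risk, as determined by an acute assessment by" a named team member. The same section says that ending the stimulation week does not end the study. It sets follow-up to week 4 with the HDRS, the YMRS and the suicide questionnaire.
- Section 2.3.1: "In the case suicide risk increases after the screening visit, the participant will be asked to stop the study". Referral and contact with the participant's doctor follow. The instrument named there is the HDRS17 suicide item: "Additionally, we will administer this as a daily questionnaire to assess suicide risk".
- Section 9.4.4, on safety analysis, says that if the questionnaire shows SI or SB, "the participant will be contacted and an acute assessment will be completed if necessary". Verified increases are then counted and compared between groups.

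On mania, section 5.1 defines a manic episode as a YMRS score above 12. Section 7.1 lists as a reason to end the intervention: "A participant has a YMRS score greater than to 12". Section 8.2.1, item 4, says that above the same score a named team member "will conduct an acute assessment to determine if the participant is experiencing mania", and that study participation stops if mania develops in the stimulation week. Section 9.4.4 treats the score as a possible episode to be assessed.

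**The concern.** This is an individual safety rule that staff may have to apply at any session, in a trial whose synopsis describes participants as having a diagnosis of depression. If the sections differ on what triggers a stop, who decides and what ends, a coordinator who follows one of them can breach another. The question that matters most is whether a participant who reports suicidal thoughts stays under safety follow-up: 7.1 says so for those who leave the intervention, while the suicidality item in 8.2.1 says nothing about it.

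There is a second, smaller consequence for the analysis. Section 9.3 admits only those who receive all five stimulation sessions, and sections 7.2 and 6.2.1 replace those who leave the study after part of the intervention and reuse their codes. An unclear stopping rule therefore makes membership of the analysis set unclear.

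**Working it through.** No figure in the plan bears on this point, so the check is a comparison of the current text.

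**Suicidality**

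| Section | Trigger | Who decides | What ends | Follow-up stated |
|---|---|---|---|---|
| 8.2.1 | Any SI or SB in past 24 hours, by self-report | Nobody named; the answer itself | Participation | None beyond contact with the participant's doctor |
| 7.1 | Increased risk | Named assessor, by acute assessment | Intervention, not the study | To week 4, three instruments |
| 2.3.1 | Increase since screening | Not stated | The study | Referral |
| 9.4.4 | SI or SB on the questionnaire | Named assessor, if necessary | No stop mentioned | Not addressed |

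Sections 2.3.1 and 7.1 share a trigger, an increase in risk, but differ on what ends. Section 8.2.1 differs from both on the trigger, and from 7.1 on the need for an assessment. Section 10.1.6 adds a further decision route: the principal investigator and/or co-investigator review adverse events in real time and decide on continuation.

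The instrument is also unsettled. Section 2.3.1 makes the HDRS17 suicide item a daily measure, whereas 8.1.3 lists the HDRS17 at the initial session, Day 1, Day 5 and the two follow-up visits. The every-session tool in 8.2.1 is a different questionnaire. (The schedule of activities cannot be read reliably in the text available.)

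**Three cases**

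1. *SI reported on Day 3; the assessment finds no increased risk.* Under 8.2.1 participation stops, so fewer than five sessions are given and 9.3 excludes the participant. Under 7.1 the suicidality item is not met. Unless another item in that list is invoked, the participant can complete and be analysed.
2. *SI reported on Day 3; the assessment finds increased risk.* All three stopping rules end stimulation, and 9.3 excludes the participant in each. Under 7.1 the participant remains in the study with follow-up to week 4; under 2.3.1 the participant is asked to leave it. Section 7.2 replaces partial recipients who leave the study, so replacement depends on which section is followed.
3. *SI first reported at the 2-week visit.* The intervention is complete, so 9.3 keeps the participant in the analysis. Under 7.1 there is no stimulation left to end; under 8.2.1 participation stops and later visits may be missing.

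**Mania**

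| Section | Meaning of YMRS above 12 | Consequence |
|---|---|---|
| 5.1 | An episode, by definition | Not eligible |
| 7.1 | Sufficient in itself | Intervention ends |
| 8.2.1 | A sign that calls for assessment | Study participation ends if mania develops in the stimulation week |
| 9.4.4 | A possible episode | Assessment; verified episodes counted |

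A score that is an episode by definition in one section needs verification in two others. No section says whether stimulation may resume or continue if the assessment is negative.

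**Reporting.** Section 9.3 names the per-protocol set as the only analysis population, and 9.4.4 names no separate safety set. Participants stopped early for these reasons could therefore be missing from the 9.4.4 group comparisons of the same events.

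**The case against.** The strongest defence is that the sections can be reconciled by reading. Section 7.1 is a list of reasons, does not say its suicidality item is the only route, and ends with a best-interest clause that could cover an 8.2.1 stop. Section 5.4 uses a stop-then-assess order at screening, so 8.2.1 might be meant the same way. This is plausible, but the text does not say it. The mania item of 8.2.1 writes in an assessment and the suicidality item does not. Nor does this reading settle whether stimulation or the study ends.

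Several stronger readings are tempting and are not supported:

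- *Four contradictory stopping rules.* Section 9.4.4 states no stopping rule for SI or SB. It adds ambiguity about assessment, not a fourth rule.
- *The same outright conflict for mania.* Sections 7.1 and 8.2.1 can be read as two steps: stimulation ends, then the assessment decides study status. The gap is the conflicting meaning of the score and the silence about a negative assessment.
- *Entry with a non-zero HDRS17 suicide item lets someone be stopped with no increase.* Section 5.1 admits scores below 3, but 5.4 places suicidal ideas or gesture above 2, and 8.2.1 uses a different question. An unchanged state that meets 8.2.1 is not shown.
- *A sized or one-sided bias.* A reader might take the figure in 2.2 of up to 25% with suicidal ideation. Assume that a share p of 72 reports SI in the stimulation week, that a share c of these is confirmed, and that a confirmed-only rule is the comparator. The difference is 72 × p × (1 − c). With p = 0.05 and c = 0.75 it is 0.9; with p = 0.25 and c = 0.25 it is 13.5. That spread comes from the assumptions. The 25% has no stated period and is not a 24-hour measure. Section 2.3.1 reports increased suicidal thoughts in 4 sham participants and none given tACS in a similar trial, but without arm sizes or timing, so one-sided exclusion before the fifth session cannot be inferred.

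Two further points stand. Exclusion and replacement come from 9.3, 7.2 and 6.2.1, and a single clear stopping rule would leave them in place. Part of the remedy also exists: withdrawal reasons are recorded, verified events are compared between groups, and 7.1 sets follow-up.

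**Conclusion.** The point holds for suicidality: 8.2.1, 7.1 and 2.3.1 cannot all be followed as written, because they differ on trigger, on whether an assessment decides, and on whether stimulation or the study ends. Section 9.4.4 adds uncertainty about assessment. For mania the finding is narrower: the meaning of YMRS above 12 is inconsistent and the consequence of a negative assessment is unstated.

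The main consequence is operational and concerns safety: who is stopped, on whose decision, and with what follow-up. The effect on the analysis set is secondary and confined to stops before the fifth session. Its size cannot be estimated from the documents, and no direction of bias is claimed. The conclusion rests on a plain reading of the current text, including that participation in the suicidality item of 8.2.1 means participation in the study, as the mania item of that section says expressly.

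**What to change.** Reconcile 2.3.1, 7.1, 8.2.1 and 9.4.4, and 5.1 for the YMRS definition, so that suicidality and mania each have:

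- one trigger, with the instrument and its schedule named;
- one decision-maker;
- one consequence, stated as end of stimulation or end of study, with an explicit statement of whether the 7.1 follow-up applies;
- for YMRS above 12, what happens if the assessment is negative.

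Which clinical rule to adopt is for the sponsor and investigators.

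In 9.4.4, add that all randomised participants stopped for these reasons will be reported by arm, with the reason and the number of sessions received, including those outside the per-protocol set.

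The cost is a protocol amendment and staff retraining. No new procedures are needed.

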8.2.2 COGNITION

1. A battery of cognitive assessments, designed to assess the cognitive deficits common in lupus, will be administered at baseline (day 1 of stimulation), day 5 of stimulation, and at both follow-up visits. This battery will be used to assess any changes in cognition following the intervention and will also be used to determine if tACS has any negative effect on cognitive abilities.

8.2.3 LABORATORY ASSESSMENTS

- **At the initial session, blood samples will be taken. These will be used to complete hematology (complete blood count, or CBC, with differential; includes white blood count, hemoglobin, hematocrit, and platelet count, which are used to score the SLEDAI 2000 assessment), as well as to assess levels of anti-dsDNA (measures levels of antibodies of double-stranded DNA, which is a diagnostic assessment of SLE) and measures of inflammation (C-reactive protein or CRP, and a complement C3/C4 panel). This same blood testing will be completed at the 4-week follow-up as well.
- **On day 1 of stimulation and at the 4-week follow-up, participants will provide a urine sample. Urinalysis, including protein/creatinine ratio and a pregnancy test (urine pregnancy lab or dipstick reading) will be assessed with this urine sample. This is for a basic assessment of overall health and is also used for the SLEDAI 2000 assessment.

**These specific assessments are imperative for completing the SLEDAI 2000. These laboratory assessments are valid for 28 days prior to the visit, so if any of these laboratories were obtained as part of routine clinical care in the preceding 28 days, they could be used to calculate the SLEDAI 2000. In clinical use, they are obtained every 3 months.

8.3 ADVERSE EVENTS AND SERIOUS ADVERSE EVENTS

8.3.1 DEFINITION OF ADVERSE EVENTS (AE)

Adverse event means any untoward medical occurrence associated with the use of an intervention in humans, whether or not considered intervention-related (21 CFR 312.32 (a)).

8.3.2 DEFINITION OF SERIOUS ADVERSE EVENTS (SAE)

An adverse event (AE) or suspected adverse reaction is considered "serious" if it results in any of the following outcomes: death, a life-threatening adverse event, inpatient hospitalization or prolongation of existing hospitalization, a persistent or significant incapacity or substantial disruption of the ability to conduct normal life functions, or a congenital anomaly/birth defect. Important medical events that may not result in death, be life-threatening, or require hospitalization may be considered serious when, based upon appropriate medical judgment, they may jeopardize the participant and may require medical or surgical intervention to prevent one of the outcomes listed in this definition. Examples of such medical events include allergic bronchospasm requiring intensive treatment in an emergency room or at home, blood dyscrasias or convulsions that do not result in inpatient hospitalization, or the development of drug dependency or drug abuse. An SAE is defined as an adverse event of grade 3 or higher as determined by the U.S. Department of Health and Human Services' Common Terminology Criteria for Adverse Events (CTCAE Version 5.0 Published: November 27th, 2017).

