7.4 SUSPENSION OR TERMINATION OF STUDY

This study may be temporarily suspended or prematurely terminated if there is sufficient reasonable cause.

Circumstances that may warrant termination or suspension include, but are not limited to:

- Determination of unexpected, significant, or unacceptable risk to participants
- Insufficient compliance to protocol requirements
- Data that are not sufficiently complete and/or evaluable
- 2 SAEs for up to 10 participants or 20% SAE if more than 10 (see SAE stopping rules below)
- 6 TEAEs for up to 10 participants or 40% TEAE if more than 10 (see TEAE stopping rules below)

If the study is prematurely terminated or suspended, the Principal Investigator (PI) will promptly inform research staff, study participants, the DSMB and the IRB and will provide the reason(s) for the termination or suspension. Study participants will be contacted, as applicable, and be informed of changes to study visit schedule.

Study may resume once concerns about safety, protocol compliance, and data quality are addressed.

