7.4.1 SERIOUS ADVERSE EVENT (SAE) STOPPING RULES

In the event of 2 SAEs (if enrollment is less than 10 subjects), possibly or definitely associated with the study intervention, the study will be suspended and the DSMB will be notified. If enrollment is more than 10 subjects, in the event of the equivalent SAEs to 20% of study enrollment, possibly or definitely associated with the study intervention, the study will be suspended and the DSMB will be notified.

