8.3.3 CLASSIFICATION OF AN ADVERSE EVENT

8.3.3.1 SEVERITY OF EVENT

All AEs will be graded for severity using the following guidelines.

- **Mild** – Events require minimal or no treatment and do not interfere with the participant's daily activities.
- **Moderate** – Events result in a low level of inconvenience or concern with the therapeutic measures. Moderate events may cause some interference with functioning.
- **Severe** – Events interrupt a participant's usual daily activity and may require systemic drug therapy or other treatment. Severe events are usually potentially life-threatening or incapacitating. Of note, the term "severe" does not necessarily equate to "serious".

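### Section 8.3.2 defines an SAE in two ways that are not reconciled, so the count of related SAEs behind the mandatory suspension rule can depend on which definition is used

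*Combined protocol and SAP*

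**What the plan says.** Section 8.3.2 contains two definitions.

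- **By outcome or judgment.** An event is serious "if it results in any of the following outcomes: death, a life-threatening adverse event, inpatient hospitalization or prolongation of existing hospitalization", and the list goes on to incapacity and congenital anomaly. The section then adds a judgment route: "Important medical events that may not result in death, be life-threatening, or require hospitalization may be considered serious". Neither route mentions a grade.
- **By grade.** The last sentence reads "An SAE is defined as an adverse event of grade 3 or higher", with CTCAE version 5.0 as the grading source.

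Section 8.3.3.1 sets the severity scale: "All AEs will be graded for severity using the following guidelines". The levels are mild, moderate and severe, and a note says that severe "does not necessarily equate to" serious. Section 8.3.4 lists what the case report form collects. It includes the clinician's severity assessment but no CTCAE grade.

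The count of related SAEs drives suspension. Section 7.4.1 begins "In the event of 2 SAEs (if enrollment is less than 10 subjects), possibly or definitely associated with the study intervention" and continues, for more than 10 enrolled, "in the event of the equivalent SAEs to 20% of study enrollment". In both cases the study is to be suspended and the DSMB told. Section 9.4.6 repeats the rule. Section 7.4 lists it as "2 SAEs for up to 10 participants or 20% SAE if more than 10". None of the three says which SAE definition applies.

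**The concern.** A suspension rule stated as a count works only if everyone counts the same events. Here the two definitions can include different events, and nothing ranks one above the other. Section 7.4.1 leaves no discretion once the count is reached, so the ambiguity passes straight into the decision.

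The grade-based sentence also relies on a quantity that the plan does not say it will record. Section 8.3.3.1 uses three named levels. The stimulation questionnaire in section 6.1.2 uses a further scale from 1 to 4, on which 3 means moderate. Neither is mapped to CTCAE grades.

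Two other provisions depend on SAE status:

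- **Reporting (section 8.3.5).** Non-fatal, non-life-threatening, unexpected, suspected serious reactions go to the IRB and the DSMB within 48 hours. An unanticipated problem that is not an SAE has 7 days, and that row does not name the DSMB.
- **Collection window (section 8.3.4).** Recording runs to 7 days after the 3-month follow-up for non-serious events and to 30 days for SAEs.

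**Working it through.** **No figure of the plan to reproduce.** The thresholds of 2 events and 20% are stated rules without a derivation. They are the same under either definition. What can change is the count compared with them.

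**Step 1: which events move.** Call the outcome-or-judgment definition A and the grade sentence B.

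| Related event | A alone | B alone (B replaces A) | A or B (B adds to A) |
|---|---|---|---|
| Grade 3 or higher, not serious by outcome or judgment | no | yes | yes |
| Important medical event by judgment, below grade 3 | yes | no | yes |
| Serious under A and grade 3 or higher | yes | yes | yes |

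If B adds to A, the only effect relative to A is more events counted. If B replaces A, events of the second kind drop out as well.

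**Step 2: thresholds.** Above 10 enrolled, trigger = 20% of enrolment, rounded up.

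- 20 enrolled: 0.20 × 20 = 4
- 45 enrolled: 0.20 × 45 = 9
- 72 enrolled: 0.20 × 72 = 14.4, so 15

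The maximum of 72 is from section 4.1. The figure of 45 is the expected number with evaluable data (sections 4.1 and 9.3). It serves here only as an interim enrolment, because the rule runs on enrolment.

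**Step 3: smallest case.** With 9 enrolled the trigger is 2. Two related grade 3 events that are not serious under A give a count of 0 under A (no suspension) and 2 under B (suspension). A single reclassified event changes the decision only when the count is one short of the trigger.

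**Step 4: illustration of size, on assumed rates.** The documents give no event rates. Assume that 5% of participants have a related event serious under A, that a further share q has a related grade 3 event not serious under A, and that each participant has at most one event. Look once, at n enrolled with trigger r. The chance of reaching the trigger is P(X ≥ r) with X binomial(n, p), where p = 0.05 under A and p = 0.05 + q if grade 3 events also count.

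For n = 9, r = 2, p = 0.05: 1 − 0.95^9 − 9 × 0.05 × 0.95^8 = 1 − 0.6302 − 0.2985 = 0.071.

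| n (trigger) | A alone, or q = 0 | q = 5% | q = 10% | q = 15% |
|---|---|---|---|---|
| 9 (2) | 7.1% | 22.5% | 40.1% | 56.4% |
| 20 (4) | 1.6% | 13.3% | 35.2% | 58.9% |
| 45 (9) | 0.03% | 3.2% | 22.5% | 55.9% |

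With q = 0 the definitions agree. The table shows how the result depends on q. It does not predict what this trial will see.

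**The case against.** The strongest reply is that the last sentence of 8.3.2 simply widens the definition. On that reading there is one broader count, no outcome-serious event is missed, and the only cost is over-inclusion. The text permits this reading but does not state it. It also sits badly with the note in 8.3.3.1 that severe and serious are different things.

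The second reply is about weight, and much of it stands. Only related events count. The protocol describes tACS effects as mild and transient (section 2.3.1) or as mild to moderate (section 7.4.2). The study can also be suspended for unacceptable risk under section 7.4, and section 10.1.6 provides real-time review by the investigators and DSMB review every 6 months. These safeguards limit the consequence without settling the count. The primary EEG analysis is not affected.

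Three stronger readings are tempting, and the documents do not support them.

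- A reader might infer that the two counts always differ. They coincide if every event serious under the first definition is grade 3 or higher and the reverse.
- A reader might infer that a moderate event leading to hospitalization is missed by the grade sentence, or that every severe event is caught by it. Both need a mapping from the three-level scale to CTCAE grades, which the protocol does not give. The judgment route in 8.3.2 is the safer example, because it requires no grade.
- A reader might infer that every reporting deadline is in doubt. The 24-hour row of section 8.3.5 turns on fatal or life-threatening reactions, and the grade sentence should not change that.

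**Conclusion.** The point holds as an internal inconsistency in the current text. Section 8.3.2 gives two SAE definitions without saying how they relate, section 8.3.3.1 conflicts with the second, and no other section resolves it. The count behind a mandatory suspension rule can therefore differ by definition. So can entry to the 48-hour reporting row and the choice between the 7-day and 30-day collection windows.

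The size is certain only as a possibility: with fewer than 10 enrolled, the same two events can give 0 or 2 SAEs. How often this would happen cannot be derived from the documents, and the percentages in the working rest wholly on assumed rates. The direction depends on the reading: over-inclusion only if the grade sentence adds to the first definition, and also missed important medical events below grade 3 if it replaces it.

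**What to change.** Reconcile sections 8.3.2, 8.3.3.1, 7.4, 7.4.1, 8.3.4, 8.3.5 and 9.4.6 so that one SAE definition feeds the suspension count, the reporting table and the collection window. The choice of definition belongs to the sponsor; nothing here favours either. State the role of the CTCAE sentence explicitly, whichever way it is settled. Record severity as a separate field on one named scale, and if a CTCAE grade is needed for any rule, collect it.

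In the same edit, align the enrolment boundary. Section 7.4 applies the 2-event rule up to 10 participants. Sections 7.4.1 and 9.4.6 apply it below 10 and the percentage rule above 10, which leaves exactly 10 uncovered.

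The cost is a wording amendment and one case report form field.
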